1) small sample sizes; 2) inadequate classification of distinct phenotypes (e.g., emphysema vs. airway disease); 3) widely varying criteria used for case definition and control selection in different studies; 4) failure to assess (and, if necessary, adjust) for population stratification; 5) testing a limited number of genetic variants in each candidate gene; 6) genotyping error; and 7) lack of correction for multiple statistical testing. Recent progress in single nucleotide polymorphism (SNP) genotyping and DNA sequencing allows for association studies on a genome-wide scale, rather than limiting analysis to recognized candidate genes or regions of linkage; however, the multiple statistical tests involved in genome-wide association (GWA) studies of thousands of SNPs raise challenges in separating true from false positive associations (6). In addition, genetic association studies within a single racial/ethnic group may not generalize to other populations.

To address the multiple testing and generalizability problems of GWA studies, we have performed comprehensive GWA, exome sequencing and whole genome DNA sequencing to identify genes influencing COPD in two major racial/ethnic groups (non-Hispanic Whites and African Americans). In Phase 2 this work will be expanded to all subjects and additional information about longitudinal change will provide important new phenotypic markers for genetic analysis particular in discerning subjects with stable or slowly progressive disease compared to those with rapid progression.

Adding to the cross-sectional subject data collected in the baseline COPDGene study visit, disease progression and incidence of COPD in smokers are important additional endpoints for genetic association studies. We have completed enrollment of 10,300 subjects as the first phase of this project and now propose to invite these subjects to return for a second evaluation five years after the initial visit to assess disease incidence and/or progression in COPDGene subjects.

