- (2) Genome-wide association and DNA sequencing studies will identify genetic determinants for COPD susceptibility that will provide insight into clinically relevant COPD subtypes.
- (3) Distinct genetic determinants influence the development of emphysema and airway disease.

Specific Aim 1: Cohort Building – Phase 1

(This Aim has been completed except for enrollment of additional non-smoking control subjects.)

Identify and phenotype up to 4,500 COPD cases GOLD Stages 2 through 4, 4,500 smokers without COPD, 1,500 GOLD Stage 1 and GOLD U subjects, and up to 1,500 non-smokers without lung disease, from two racial/ethnic groups (non-Hispanic Whites and African Americans) for genetic, epidemiologic, and natural history studies.

Specific Aim 2: Genome-Wide Association Study – Phase 1 and 2

(Analytic work is in progress.)

- a. Stage 1. A genome-wide panel of SNPs will be tested for association with COPD in case-control samples from non-Hispanic Whites and African Americans.
- b. Stage 2. Fine mapping of candidate genes to identify susceptibility alleles and/or high risk haplotypes using multiple study designs and independent samples, including:
 - Entire set of case-control samples from both racial/ethnic groups
 - External validation using family-based association analysis in the Boston Early-Onset COPD Study and the International COPD Genetics Network.
- c. Stage 3 (Part of Phase 2 of COPDGene). We will genotype the Exome Chip (Illumina, Inc.) in all COPDGene smokers and test for rare and common variant associations with baseline and longitudinal COPD-related phenotypes. We will perform whole sequencing of subjects with distinct imaging characteristics to identify rare and common genetic variants influencing COPD susceptibility, emphysema, and airway disease.

Specific Aim 3: Characterization of Subtypes of COPD – Phase 1 and 2

(Analysis in progress.)

- a. To further characterize the unique airway and parenchymal phenotypes of COPD by determining their associations with clinical, physiologic and functional indices.
- b. Identify susceptibility genes for COPD subtypes, including CT-defined emphysema and CT-defined airway disease.

Specific Aim 4: Natural History of COPD and Risk Factors for Progression

The five-year natural history and progression will be completed in Phase 2.

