- a. Five years after the initial clinical evaluation, a second visit will be performed in all subjects enrolled in the study to assess disease status based on clinical, physiological, and chest CT assessments similar to the initial study visit.
- b. The cohort will also continue to be followed longitudinally with telephone questionnaires every six months to determine mortality, COPD exacerbations, current cigarette smoking and co-morbid disease events.

Subject Selection

We are recruiting up to 12,000 smoking and non-smoking subjects.

Subject Inclusion/Exclusion Criteria for Phase 1 Data

A total of 12,000 non-Hispanic White and African-American subjects will be or have been recruited. Data from the Phase 1 study visit has been stored in the Data Coordinating Center. Biological specimens have been stored at the Johns Hopkins Biorepository and at the Brigham and Women's Hospital Biorepository. CT images have been stored in the National Jewish Imaging Core as well as the Brigham and Women's Hospital and University of Iowa Imaging Cores.

Phase 1 Actual Enrollment:

Phase 1, which was performed from November 2007 until July 2012, enrolled 10,364 subjects. Of these subjects 3416 were African American and 6884 were Non-Hispanic White. Enrolled subjects classified by severity of lung disease were as follows:

- Smoker Controls – 4388
- GOLD 2 - 4 Subjects – 3690
- GOLD Unclassified – 1257
- GOLD 1 Subjects – 794
- Non-smokers controls – 108
- Lack final GOLD classification due to failed spirometry – 63
- Significant ILD noted on CT scan, excluded from analysis – 64

Inclusion Criteria for the COPDGene Central Study Protocol:

Enrollment in the COPDGene study at any of the twenty one clinical centers with subject identifiers and protected health information uploaded to the Data Coordinating Center.

Exclusion Criteria:

None, if the inclusion criterion is met

Enrollment of up to a total of 1700 additional non-smoker controls is anticipated in Phase 2.

Study Procedures Related to COPDGene Central Study Components

During the Phase 2 research study visit, the following procedures will be performed at the local Clinical Centers but are related to Central Study functions. Local Clinical Center functions are described to provide a context for the Central Study functions.

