In Phase 1, genome-wide association analysis will be performed using genome-wide SNP genotyping data that has been obtained in the entire COPDGene study population. In Phase 2, exome chip genotyping, whole genome sequencing, and targeted sequencing data will be obtained. For exome chip and targeted sequencing data, analyses will be performed on a gene level, while for whole genome sequencing, sliding windows of 20 SNPs will be used. For rare variant analysis, we plan to use three analytical approaches to analyze non-synonymous SNPs—the Combined Multivariate and Collapsing Method (CMC) (14), the Morris and Zeggini (M-Z) likelihood ratio method (15), and a powerful weighted, permutation-based approach (16). For all three of these approaches, analyses will be performed at the gene level, using only nonsynonymous variants with allele frequencies < 0.05. We recognize that selection of this 5% threshold to define a rare SNP is arbitrary; therefore, we will also perform exploratory analyses using a lower allele frequency threshold of 1% as well as an analysis of all detected SNPs, regardless of allele frequency. Due to differences in genetic background, separate analyses will be performed in NHW and AA subjects.

In addition to rare variants, Exome Chip genotyping and whole genome and targeted sequencing will also identify common non-synonymous and other functional variants. Single common variant associations to baseline and longitudinal COPD-related phenotypes will be assessed using regression analysis in PLINK, separately in non-Hispanic Whites and African Americans, with adjustment for age, gender, pack-years, and principal components of global genetic ancestry (17). Although our primary focus will be on single SNPs, copy number variants will also be assessed for association to COPD and COPD-related phenotypes.

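### Common variants are assessed only in separate NHW and AA regressions, with no step that combines or compares the two groups, which gives up power for shared loci and leaves generalizability untested

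*Protocol*

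**What the plan says.** Protocol, Background and Significance, names two difficulties with genome-wide studies. One is telling true from false positives among very many tests. The other is that "genetic association studies within a single racial/ethnic group may not generalize to other populations". It then says: "To address the multiple testing and generalizability problems of GWA studies, we have performed comprehensive GWA, exome sequencing and whole genome DNA sequencing", in NHW and AA subjects, with the work to be extended to all subjects in Phase 2. The same section makes finding new loci a primary goal of Phase 2.

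Biostatistical Analysis says that single common-variant associations with baseline and longitudinal phenotypes "will be assessed using regression analysis in PLINK, separately in non-Hispanic Whites and African Americans", adjusted for age, gender, pack-years and ancestry principal components. Rare-variant analyses are split as well: "Due to differences in genetic background, separate analyses will be performed in NHW and AA subjects". No step joins or compares the two sets of results.

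Specific Aim 2, Stage 2, describes the follow-up: "Fine mapping of candidate genes to identify susceptibility alleles and/or high risk haplotypes using multiple study designs and independent samples, including" the "Entire set of case-control samples from both racial/ethnic groups", and external family-based validation in two named outside studies.

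On group sizes, Phase 1 Actual Enrollment states: "Of these subjects 3416 were African American and 6884 were Non-Hispanic White".

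**The concern.** The common-variant paragraph is not silent on method. It fixes the software, the covariates and the split by group. Followed as written, it produces two lists of results and no joint estimate.

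Two things are at stake. First, a locus with the same modest effect in both groups may reach a genome-wide threshold in neither scan, although the whole cohort would detect it. That works against the goal of finding new loci. Second, generalizability is a question about whether an effect in one group is also present in the other. Two separate lists do not answer it, and the AA group, at half the size, will often be non-significant for loci that are shared.

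**Working it through.** **Inputs from the protocol.** NHW 6,884; AA 3,416; sum 10,300. Cases (GOLD 2–4) 3,690; smoker controls 4,388. The protocol gives no power figure for common variants (Table 1 covers rare variants only), so there is no stated figure to reproduce.

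**Assumptions not in the protocol.** Two-sided 5e-8, critical value c = 5.451. Same effect, allele frequency and case mix in both groups, so information is proportional to group size: r = 3,416/6,884 = 0.496, √r = 0.704, √(1+r) = 1.223.

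**Formulas.**
- Expected NHW statistic: z_N = c + Φ⁻¹(NHW power)
- AA: z_A = z_N × √r
- Fixed-effect combination: z_C = z_N × √(1+r)
- Power = Φ(z − c)
- Either scan = 1 − (1 − P_N)(1 − P_A), since the groups are different people

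| NHW power | z_N | z_A | z_C | AA power | Either scan | Combined |
|---|---|---|---|---|---|---|
| 80% | 6.293 | 4.433 | 7.698 | 15% | 83% | 99% |
| 50% | 5.451 | 3.840 | 6.668 | 5% | 53% | 89% |
| 33% | 5.011 | 3.530 | 6.130 | 3% | 35% | 75% |

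**Check by a second route.** Allelic two-proportion test, with cases and controls divided in the ratio 6,884:3,416 (about 2,466 and 2,933 in NHW). The protocol does not give this split by race. For minor allele frequency 0.2 and odds ratio 1.25, the case frequency is 0.25/(0.80 + 0.25) = 0.2381. The pooled frequency is 0.2174 and the standard error 0.00797, so z_N = 0.0381/0.00797 = 4.78. Then z_A = 3.37 and z_C = 5.85, giving powers of 25% (NHW), 2% (AA), 27% (either) and 65% (combined). At the same allele frequency:
- odds ratio 1.30: 61% either, 93% combined
- odds ratio 1.40: 98% either, above 99% combined

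So the gain is for modest effects and is negligible for large ones.

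**If the groups differ.** Let the AA effect be k times the NHW effect. Then z_C = z_N(1 + kr)/√(1+r). With NHW power 80%:
- k = 0.5: z_C = 6.42, combined 83% against 80% for the separate scans, so little is gained
- k = 0: z_C = 5.14, combined 38% against 80%, so combining loses

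**Reading generalizability from AA significance.** In the 80% row, a shared locus reaches 5e-8 in AA 15% of the time, so a miss there says little. If instead ten NHW lead SNPs are tested in AA at 0.05/10 = 0.005 (critical value 2.807), a shared one is confirmed with probability Φ(4.433 − 2.807) = 95%.

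**Paying for a third test.** Dividing 5e-8 by three gives c = 5.643. Combined power becomes 98% / 85% / 69%. The NHW scan alone falls from 80% / 50% / 33% to 74% / 42% / 26%.

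**The case against.** A reader might infer that the plan has no replication, or that neither stated purpose is met. The protocol does not support that. Aim 2 Stage 2 uses independent samples, both groups' case-control samples and two external family-based studies. This bears directly on false positives, and studying both groups bears in part on generalizability. What stands is narrower: Stage 2 is described as fine mapping of candidate genes, so it starts from what Stage 1 found, and no between-group comparison is stated there.

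A reader might also infer that group-specificity will be declared from significance in one group only, or that two scans double the false positives. The protocol states no such rule and no threshold. Two independent scans each held at 5% would give 1 − 0.95² = 9.75% jointly, but only if a hit in either counts without adjustment.

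The separate-regression sentence follows one about variants found by the Phase 2 platforms. The Phase 1 genome-wide analysis has its own sentence, with no split attached. The point is therefore firmest for the Phase 2 common-variant work.

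Stratified regression with ancestry components is a sound guard against confounding by ancestry, and it is the natural first step of a meta-analysis, which the protocol does not exclude. Thresholds and heterogeneity statistics may properly sit in an analysis plan that is not shown, so their absence is not in itself an error. The objection does not remove the mismatch between the purpose given for two groups and an analysis paragraph that fixes the split and stops there.

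**Conclusion.** The point holds as a worthwhile improvement, not as a failure of the design. As written, the common-variant analysis forgoes power for modest effects shared by both groups: 53% against 89% when NHW power is 50%, and 35% against 75% when it is 33%. It also leaves generalizability without a test. These figures rest on an assumed 5e-8 threshold and on equal effect, allele frequency and case mix. Differences in effect or linkage disequilibrium would shrink the gain. It is close to nil at half the NHW effect and reverses if AA has no effect.

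**What to change.** In Biostatistical Analysis:

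1. Keep the separate NHW and AA regressions, with their ancestry components, as reported results.
2. Add an inverse-variance meta-analysis of the two sets of estimates.
3. Set one study-wide threshold that accounts for the NHW, AA and combined tests, for example 5e-8 divided by three.
4. For each lead SNP, report Cochran's Q and test it in the other group at 0.05 divided by the number of leads.
5. State that group-specificity will not be inferred from significance in one group only.
6. Say how these results feed Aim 2 Stage 2.

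**Cost.** A summary-statistics step on results already produced, with no new data. The separate scans face a somewhat stricter threshold (the NHW scan falls from 80% to 74% in the first case above). A fixed-effect combination is also less sensitive to loci acting in one group, which is why the separate results stay alongside it.

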The COPDGene study has a central Administrative Core that coordinates the study activities and works closely with the Data Coordinating Center to write and communicate the study protocol, consent template, manual of operations and to oversee training of the clinical center staff involved in the study. The Administrative Core also manages investigators meetings, provides scheduling and coordination for committee meetings and writing groups, oversees the longitudinal follow-up program, manages acquisition of Medicare cost information, performs Social Security Death Masterfile (SSDMF) searching and maintains the study files for death adjudication.

The Imaging Core receives subject CT scan image files and clinical center phantom data files along with dates of CT scan. The Imaging Core assesses the quality of the CT images and performs analysis of quantitative characteristics on the image files as well as overseeing the more complex scoring of images for visual analysis. Data and image files are shared between the three different sites (National Jewish Health, University of Iowa and Brigham and Women’s Hospital) under the Imaging Core. Final output from the image analysis work is transferred and stored in the DCC

The Pulmonary Function Testing (PFT) Core receives subject data with a date of study visit from the twenty one clinical centers via a file depot located at National Jewish provided by the Data Coordinating Center. [name] is the head of the PFT Core. He reviews the Spirometry and DLCO data for quality assessment and returns this data with a quality grade to the Data Coordinating Center. A back up data handling process for PFT quality assurance is located at National Jewish Health with [name] providing quality grading.

The Sample Storage Cores (Biorepositories) for COPDGene are located at Johns Hopkins University (JHU) and Brigham and Women's (BWH) Hospital. In phase 1 of the study biospecimens and DNA were stored at JHU, and in phase 2 of the study, biospecimens will be stored at BWH. Backup storage of DNA from phase 1 is already in place at BWH. The date of sample collection is part of the information stored at each site. All samples are otherwise stored with a code but no other identifiers. The coded identifier for both sites is the COPDGene subject ID number.

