Subjects will continue to be contacted up to four times per year by telephone, mail, or email for up to 10 years. Questions will be asked about current health status, exacerbations, cancer, new illnesses or medical conditions and current smoking status. The longitudinal follow-up contact mechanism is primarily based on automated contacts to subjects via a computer server controlled by the local clinical center in which the clinical center securely uploads subject contact data and social security number to a secure server using secure sockets (SSL) technology and 128 bit or greater encryption with an HTTPS protocol. Subjects establish a preference for contact by email and web data entry or automated phone calls with data entry by telephone keypad. Subject contact information and identifying information is deleted automatically from the server after the contact is made or at the end of three weeks. Data collected from the subjects is de-identified and made available to the Data Coordinating Center at National Jewish to be stored. Subjects who fail to respond to automated contacts are contacted by the local clinical coordinator who then completes the clinical questions for the subject into the web-based data collection form. Subjects who become lost to follow-up from the longitudinal follow-up process are traced by their secondary contacts and searched for in the social security death index using the same automated server system querying the social security master death file. Deaths identified from the social security death search are communicated to the Data Coordinating Center and the local clinical center. The local clinical center initiates collecting further information about the death as described below.

Central Study Function: In the event that the local clinical center is unable to complete the longitudinal follow process for their subjects the COPDGene central Administrative Core will take over that function using the stored subject personal identifiers to upload subject information to the computer server and will complete follow-up coordinator phone calls to subjects.

Communications to Study Subjects

In addition to the longitudinal follow-up program of phone and email contacts, Subjects may be contacted on no more than three additional occasions per year to inform them of other research studies and to update them about results of the COPDGene study. In general these contacts will be made through staff at the local clinical center.

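### The stated covariate set omits clinical centre and baseline smoking status, and has no term for time between visits, giving up some precision for quantitative CT and change phenotypes

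*Protocol*

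**What the plan says.** The protocol (Biostatistical Analysis) states one regression for common variants: "Single common variant associations to baseline and longitudinal COPD-related phenotypes will be assessed using regression analysis in PLINK", fitted separately in the two racial groups, "with adjustment for age, gender, pack-years, and principal components of global genetic ancestry". The same list serves baseline and longitudinal phenotypes. That sentence does not name CT, but Specific Aim 3 makes CT measures genetic endpoints: "Identify susceptibility genes for COPD subtypes, including CT-defined emphysema and CT-defined airway disease". The Phase 2 goals also include progression and reclassification by imaging.

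What the study holds on the omitted items:

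- **Smoking status.** The cohort is described as a mix of current and former smokers, and the Phase 1 questionnaires covered smoking history. Specific Aim 4 provides for "telephone questionnaires every six months to determine mortality, COPD exacerbations, current cigarette smoking and co-morbid disease events", and the Longitudinal Follow-Up section also lists "new illnesses or medical conditions and current smoking status".
- **Centre.** Every subject ID carries a three-letter centre code (Data Collected and Data Handling). There are 21 centres.
- **Scanner.** The Imaging Core receives "clinical center phantom data files along with dates of CT scan" (Structure of the Central COPDGene Study). Scanner make or model is not named as a data item.
- **Time between visits.** The section on Imaging Core procedures treats the scan date as essential for comparing the two visits. Specific Aim 4 plans the second visit at five years, with no window.

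**The concern.** Pack-years is a cumulative measure. It cannot separate a subject who smokes now from one with the same total who has stopped. CT measures from 21 centres may differ for reasons of equipment and subject mix, and the collection of phantom files by centre suggests the study expects this. An unadjusted difference between two visits also depends on how far apart they were.

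If such determinants are left in the residual, each SNP effect on a quantitative CT or change phenotype is estimated with a larger standard error than necessary. The phenotypes affected serve the main Phase 2 goals, and the missing terms are cheap to add.

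**Working it through.** The protocol states no sample size, alpha or power for this regression. Its Table 1 comes from a rare-variant case-control simulation, so there is no figure to reproduce. The subject counts are from Phase 1 Actual Enrollment: 6,884 non-Hispanic White and 3,416 African American. Fewer will have change data, since a second visit is needed. All variance shares below are assumptions.

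**1. Precision (linear models).** Let R² be the share of residual variance explained by the added terms. The standard error is multiplied by √(1 − R²), and the gain in effective N is 1/(1 − R²) − 1.

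| Assumed R² | Reduction in SE | Gain in effective N |
|---|---|---|
| 3% | 1 − √0.97 = 1.5% | 1/0.97 − 1 = 3.1% |
| 5% | 1 − √0.95 = 2.5% | 1/0.95 − 1 = 5.3% |
| 10% | 1 − √0.90 = 5.1% | 1/0.90 − 1 = 11.1% |

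At an assumed two-sided alpha of 5 × 10⁻⁸, a variant with 80% power under the present model would have 84% at R² = 5% and 88% at R² = 10%, in either racial group.

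**2. Cost of centre terms.** Twenty-one centres use 20 degrees of freedom: 20/6,884 = 0.3% and 20/3,416 = 0.6%. Centre therefore repays its cost once it explains more than roughly those shares of residual variance.

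**3. Does omitting centre confound?** Only if allele frequency still differs between centres after the race split and the ancestry components. Let F be that remaining between-centre share of genotype variance, and C the between-centre share of phenotype variance. With 21 equal centres, the test statistic is inflated by about 1 + N·F·C/21. At N = 6,884:

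- F = 0: inflation 1.00 whatever C is (simulated 0.98 at C = 10%, Monte Carlo SE 0.03).
- F = 0.001, C = 5%: 1 + 6,884 × 0.001 × 0.05/21 = 1.02 (simulated 1.03).
- F = 0.005, C = 10%: 1 + 6,884 × 0.005 × 0.10/21 = 1.16 (simulated 1.14, and 1.02 after centre adjustment).

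For a single SNP, take a centre-effect SD of 0.3 phenotype SD and a SNP correlation of 0.02 with the centre effects. The shift in z is 0.02 × 0.3 × √6,884 = 0.50, against about 5.45 needed at the assumed alpha.

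**4. Time between visits.** Let m be the mean yearly decline, s the SD of the rate, e the measurement SD at each visit, and let the interval be uniform on 5 ± h years, so Var(T) = h²/3. The share of the variance of change due to unequal intervals is m²·Var(T) / [m²·Var(T) + s²(25 + Var(T)) + 2e²]. With s = 40 units per year:

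- h = 1: 533/(533 + 40,533 + 45,000) = 0.6% (m = 40, e = 150), up to 1,200/(1,200 + 40,533 + 20,000) = 1.9% (m = 60, e = 100).
- h = 2: 2.4% and 7.2% for the same two settings.

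The protocol gives no spread of intervals. Its calendar does show that some departure from five years is unavoidable: subjects enrolled in November and December 2007 reached five years before Phase 2 opened in 2013.

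**The case against.** The strongest reply is that one summary sentence covering all phenotypes does not exclude further covariates, and that scanner terms and the definition of change are details usually left to an analysis plan. This stands in part. Nothing in the protocol forbids annualizing, and it contrasts slow with rapid progression, which is the language of rates. But the sentence does state a covariate list and applies it to longitudinal phenotypes by name, so the point concerns a stated choice and not a silence.

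Three further objections stand and limit the point:

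- **The gain is assumed.** No passage supports 3% to 10%, and the fall in standard error is modest. The formula is for linear models and does not carry over directly to case-control logistic analyses.
- **Scanner correction may already happen.** The Imaging Core could correct for scanner from the phantom data before the regression. The protocol does not say whether it does.
- **Smoking is measured after genotype.** People may stop because they are ill, so conditioning on change in smoking between visits can introduce bias as well as remove a mediated effect.

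A reader might infer three stronger things. The first is that omitting centre leaves confounding that will appear as genetic signals. The documents do not show this: race stratification and ancestry components are both specified, and the illustrative z shift of 0.5 cannot by itself produce a genome-wide finding. A chance correlation of 0.02 is also only 0.02 × √6,884 = 1.7 standard errors, and the nominal standard error already allows for chance correlation. The second is that Phase 2 running over several years makes intervals unequal. Enrolment also ran over several years, and each subject's visit is planned at five, so the calendar span alone implies little. The third is that every missing covariate is already in the database. That fails for scanner model, and the interval has to be derived from dates.

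**Conclusion.** The point holds as one of precision, for quantitative CT and change phenotypes only. The stated covariate set omits centre and baseline smoking status, which the study holds, and makes no provision for time between visits. The loss is about 3% to 11% in effective N if these terms explain 3% to 10% of residual variance; the true share cannot be derived from the protocol. Residual centre confounding is possible but not demonstrated, and is negligible unless allele frequencies still differ appreciably between centres after the adjustments already planned. No planned result is invalidated. The case for change is that some power for the main Phase 2 goals is given up when recovering it costs little.

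**What to change.** For quantitative phenotypes only:

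- Add clinical centre, which also serves as a proxy for scanner. For CT measures, a phantom-based correction could be used instead if one is available; state whether the Imaging Core already applies it.
- Add current versus former smoking at the baseline visit.
- For change phenotypes, either analyse annualized change or include years between visits, derived from the recorded dates.
- Report the present model (age, gender, pack-years, ancestry components) alongside.
- Adjust for change in smoking between visits in a sensitivity analysis only.

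If the sponsor prefers the present set, it should say why these terms are left out.

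The work is a few covariate columns in runs already planned. The statistical cost is about 20 degrees of freedom per racial group, plus one or two for smoking and interval. Loci that act through smoking will be partly adjusted away, as already happens with pack-years; showing both models lets a reader see where this occurs.
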